### **Objective I: Statistics**

All data analyses will be based on the intention-to-treat principle using SPSS statistical software, unless otherwise noted. Data will be examined quantitatively and graphically for outliers and other artifacts that might have an undue impact on the analyses. Logarithmic or similar transformations will be applied when necessary to insure the validity of statistical procedures. All tests will be two-sided and considered statistically significant at  $p < 0.05$ .

### Physiological outcomes

Mixed-model repeated measures ANOVA will be used to test the effects of testosterone maintenance on changes in body composition, skeletal muscle function, protein dynamics, metabolism, and biomarkers of physiological status. Mixed-models will include subject as a random factor, study day and group as fixed factors, and the day-

by-group interaction. Akaike's information criterion will be used to determine appropriate covariance structures. When a statistically significant time-by-group interaction is detected ( $P < 0.05$ ), all possible within- and between-group comparisons will be completed, and the familywise error rate adjusted using the Bonferroni correction.

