### **Inclusion and Exclusion Criteria**

#### **Inclusion Criteria**

- Men aged 18-39 years
- Physically active (at least 2 days per week aerobic and/or resistance exercise)

- Not taking any prescription medications and/or willing to refrain from all medication use prior to and throughout the entire study period, unless provided/approved by the study physician
- Willing to refrain from alcohol, smoking, e-cigarettes or use of any nicotine product, caffeine, and dietary supplement use throughout the entire study period.
  - At the discretion of the study physician, wash-out period for medications, supplements, and over the counter medications (OTCs) is  $\geq$  1-4 weeks
  - Wash-out period for caffeine and alcohol is  $\geq$  7 days
- Willing to live on the PBRC inpatient unit for 28 consecutive days
- Willing to have a urine drug screening
- Meets age-specific US Army body composition standards according to Army Regulation 600-9, which includes estimates of percent body fat based on height, weight, and circumference measures (neck and waist)
- Total testosterone concentration is within the normal physiological range (300-1,000 ng/dL).

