## Randomization

Immediately following phase 1 testing on day 14, participants will be randomized to one of two experimental groups, either a 28-d (live-in), 55% energy deficit phase (DEF) or a 28-d (live-in), 55% energy deficit phase with exogenous testosterone administration (DEF+TEST). A randomization scheme will be determined using a block design (n=60) and age stratification (< 29 years or ≥ 29 years). Randomization will be done by a biostatistician with no direct study affiliation. Prior to the start of the study, the randomization schedule will be given to the pharmacist. The PBRC clinical research pharmacist will have no direct contact with participants. Treatment administration will be performed by a physician assistant, nurse practitioner, or nurse who will not be aware of treatment assignments. Participants and all study personnel will be blinded to treatment group. The code will be kept as a locked electronic file on a secure server by the pharmacist until study completion or there is a need to break the code for safety of the participant.

## Phase 2: 55% Energy Deficit (live-in diet & activity control). Day 15–Day 42

- During the energy deficit phase, participants will live on Pennington Biomedical's inpatient unit in a 24-hour-a-day controlled setting. Once a day, participants will have their vitals (BP, pulse) measured. All meals will be eaten on the unit and monitored. Daily, participants will be weighed. Additionally, a wrist-worn accelerometer will be used throughout phase 2.
- Throughout phase 2, participants will complete supervised exercise sessions 1-4 times per day. Every 2 weeks, participants will undergo submax met carts for each mode of exercise utilized.
- Participants will consume 100 mL/d  $^2\text{H}_2\text{O}$  (i.e., heavy water) from day 15 to 42.
- Participants will be asked to provide a saliva sample on days 15, 19, 23, 27, 31, 35, and 39 to assess body water enrichment.
- Blood draws will occur on days 28 and 42.
- Cognitive testing will be performed on days 15, 20, 22, 27, 29, 34, 36, 40 and 41 over a 1.5-2 hour period each day.
- A DXA scan will be done on days 28 and 39.
- A 1 hour fMRI will be done on days 36, 37, and 38.
- An injection (placebo or testosterone) will be administered on days 15, 21, 28, and 35.
- Eating Inventories (TFEQ, FCI, FCI trait) will be completed on day 42.

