## Objective II: Statistics

Individualized scale scores from each of the questionnaires, the MMPI-2, and the RTMITE, the scores from the Ultimatum Game, the number of points earned on the Balloon Task, and dependent measures (such as accuracy scores and reaction times) on the vigilance, memory, and reasoning tasks will be analyzed with a series of mixed-factorial ANOVAs. Significant main effects and interactions will be pursued with Analysis of Simple Effects followed by appropriate linear contrasts and pairwise comparisons.

On all assessments there will be 2 levels of the grouping factor: Intervention (Energy Deficit-Androgen Maintenance and Energy Deficit+Androgen Maintenance). For preliminary examination of immediate pre/post-dose effects (on tests other than MMPI), the primary analysis will include the single grouping factor of Intervention with two within-subjects factors: Dose-iteration (Dose2, Dose3, Dose4) and Pre-post (Pre-dose, Post-dose). For examination of cumulative treatment effects (on tests other than MMPI), the primary analyses will include the Intervention grouping factor (Energy

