#### Physiological outcomes

Mixed-model repeated measures ANOVA will be used to test the effects of testosterone maintenance on changes in appetite, postprandial endocrine responses, intestinal permeability, and SCFA concentrations over time. Postprandial appetite ratings and responses of endocrine mediators of appetite will be summarized using area under the

curve and peak/nadir concentration prior to analysis. Mixed-models will include subject as a random factor, study day and group as fixed factors, and the day-by-group interaction. Akaike's information criterion will be used to determine appropriate covariance structures. When a statistically significant time-by-group interaction is detected ( $P < 0.05$ ), all possible within- and between-group comparisons will be completed, and the familywise error rate adjusted using the Bonferroni correction.

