#### Psychological outcomes

Questionnaires will be scored according to questionnaire-specific procedures. Scores will then be analyzed by mixed-model repeated measures ANOVA. Mixed-models will include subject as a random factor, test session or study day and group as fixed factors, and the session-by-group or day-by-group interaction. Akaike's information criterion will be used to determine appropriate covariance structures. When a statistically significant time-by-group interaction is detected ( $P < 0.05$ ), all possible within- and between-group comparisons will be completed, and the familywise error rate adjusted using the Bonferroni correction.

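### Randomisation is stratified by age, but no planned model comparing the arms includes the age stratum; adding it with a stratum-by-day term is a small, nearly free gain.

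*Combined protocol and SAP*

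**What the plan says.** The Randomization section states: "A randomization scheme will be determined using a block design (n=60) and age stratification". The cut is at 29 years, and the Inclusion Criteria admit "Men aged 18-39 years". The block size within each stratum is not clearly stated: the figure of 60 may be a block length or simply the number randomised.

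The analysis sections list their model terms explicitly, and age is never among them:

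- Objective I, Physiological outcomes: "Mixed-models will include subject as a random factor, study day and group as fixed factors", with their interaction.
- Objective II: Statistics: "On all assessments there will be 2 levels of the grouping factor: Intervention". The other factors are all within-subject (dose iteration, pre/post dose, session). The sleep and fMRI analyses use intervention by period.
- Objective III A-B, Physiological outcomes: "Mixed-models will include subject as a random factor, study day and group as fixed factors, and the day-by-group interaction".
- Objective III A-B, Psychological outcomes: "Mixed-models will include subject as a random factor, test session or study day and group as fixed factors", with their interaction.
- Objective III A-B, gut microbiota and metabolomics: study day, group and their interaction.

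The Power analysis section and Table 2 size the trial on change in lean body mass: 3.0 against 2.25 kg lost, SD 0.75 kg, effect size 1.0, alpha 0.05, power 0.90. This gives 22 per group, raised to 25. No variance is removed for age or any other covariate.

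**The concern.** Stratified randomisation forces the arms to be similar in age group. If age group predicts an outcome, this balance reduces the true variance of the difference between arms. A model without the stratum leaves the age variation in the residual, so it estimates the variance as if the balance had not been arranged. The standard error is then larger than the true one, and the test rejects less often than its nominal level.

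The test of interest here is day by group, that is, a comparison of changes. The relevant question is therefore whether age group predicts change, not level. A constant difference in level between younger and older men is already taken up by the random subject effect.

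At stake is a little precision in a trial of about 25 completers per arm with many outcomes, of which only lean body mass has a stated power. There is also a point of good order: a plan that randomises within age groups but is silent on age in the analysis leaves that choice open until the data are seen.

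**Working it through.** **Inputs from the documents.** Difference 0.75 kg, SD 0.75 kg, alpha 0.05, power 0.90 and 22 per group (Table 2); two-sided testing (Objective I: Statistics); 25 completers per group (Power analysis).

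**Assumed input.** R², the share of the variance of change explained by the age stratum. The documents give no value, so I take 0 to 0.10.

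**1. The plan's own figure.** n per group = 2 × (1.960 + 1.282)² × (0.75/0.75)² = 21.0, rounded up to 22. It reproduces with no age adjustment. Power by the noncentral t is 0.900 at 22 per group and 0.934 at 25.

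**2. Effect of adjustment by formula, 25 per group.** The residual SD becomes 0.75 × √(1 − R²), with one degree of freedom spent. The ratio of unadjusted to adjusted standard error is 1/√(1 − R²). The unadjusted power is 0.934 throughout.

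| R² | SE ratio | Adjusted power |
|---|---|---|
| 0 | 1.000 | 0.934 |
| 0.01 | 1.005 | 0.936 |
| 0.02 | 1.010 | 0.938 |
| 0.05 | 1.026 | 0.944 |
| 0.10 | 1.054 | 0.955 |

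**3. What those R² values require.** With equal strata, the age-group gap in lean mass change is 2 × 0.75 × √R². This is 0.34 kg at R² = 0.05 and 0.47 kg at R² = 0.10, or 45% and 63% of the whole hypothesised treatment effect of 0.75 kg. Unequal strata would need a larger gap.

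**4. Simulation of the change-score comparison.** 50 completers, strata equally likely, blocks of 4 within strata; 20,000 trials for type I error and SEs, and 10,000 for power.

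| R² | Mean SE, unadjusted / adjusted | Type I error, unadjusted | Power, unadjusted / adjusted |
|---|---|---|---|
| 0 | 0.211 / 0.211 | 0.050 | 0.930 / 0.930 |
| 0.05 | 0.211 / 0.206 | 0.045 | 0.935 / 0.942 |
| 0.10 | 0.212 / 0.200 | 0.041 | 0.946 / 0.956 |

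The unadjusted test also gains something from the stratified design, so the realised difference in power is about 1 percentage point or less. The limiting formula 2 × [1 − Φ(1.96/√(1 − R²))] gives 0.044 and 0.039 for R² = 0.05 and 0.10. It assumes perfect balance within strata and so slightly overstates the conservatism.

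With one block of 60 per stratum, balance among 50 completers is looser. The unadjusted type I error is then 0.045 at R² = 0.05 and 0.048 at R² = 0.10. The simulation error is √(0.05 × 0.95/20,000) ≈ 0.0015, so the order of these two figures means little.

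**5. Which term does the work.** I fitted random-intercept models to 30 simulated data sets with two time points, complete data and an assumed 0.47 kg age-group gap in change. The mean standard error of day-by-group was 0.2226 with no age term, 0.2226 with a stratum main effect, and 0.2095 with stratum-by-day added. Only the interaction term helps, because the subject effect already absorbs a constant age difference.

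**The case against.** The strongest reply is that nothing here threatens validity. Without the stratum, the comparison remains unbiased and is at worst slightly conservative. If being under or over 29 does not predict change among men of 18 to 39, nothing is lost, and the documents give no evidence on how strongly it does. The R² values that matter need age gaps about half the size of the treatment effect. If the blocks are large, much of the conservatism goes. The figures above also describe a single change score, whereas the plan tests a day-by-group interaction over several visits (six for DXA). All of this stands, and it makes the point minor.

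A reader might go further and infer that the planned standard errors are definitely too wide, or that power already paid for is being thrown away. The documents support neither. The first depends on an R² that they do not give. The second fails because Table 2 took no credit for stratification: its 22 per group reproduces without age, and 25 per group gives about 93% unadjusted. What is forgone is a gain that was never counted. It would be somewhat larger at a smaller effect: at an assumed effect size of 0.7, which is not in the documents, power would move from 0.679 to 0.701–0.724 for R² of 0.05 to 0.10.

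The reply does not remove the gap in specification. Age is the only stratification factor, the plan lists its model terms in detail, and the stratum is missing from all of them.

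**Conclusion.** The point holds as a minor one. The stratification factor is absent from every planned model comparing the arms. If the stratum explains 0 to 10% of the variance of change, the unadjusted standard error is 0–5% too large. With small blocks the nominal 5% test runs at about 5.0% to 4.1%, and closer to 5% if blocks are large. At 25 per arm and effect size 1.0, power by formula moves from 0.934 to between 0.934 and 0.955. The range for R² is an assumption. The sizes apply to lean mass change analysed as a two-group comparison; those for the cognitive, appetite and microbiome outcomes cannot be derived from the documents.

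**What to change.** In Objective I (Physiological outcomes), Objective II: Statistics, and the physiological, psychological and gut microbiota parts of Objective III A-B, add to every model that compares the arms:

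- the age stratum as used at randomisation (under 29, 29 or over) as a fixed factor; and
- its interaction with study day, or with session or period where that is the time factor.

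The interaction is what sharpens the day-by-group test. The main effect belongs with it, and is of use where group main effects are also tested, as in Objective II and the taxa models. State the block size within strata in the Randomization section.

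The cost is wording, with no new data. The stratum takes one degree of freedom and the interaction one fewer than the number of time points; for the six DXA scans that is 1 + 5 = 6. If age turns out to be unrelated to change, power at 25 per group stays at 0.934 by the formula above.

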### Power analysis

Relevant data (means  $\pm$  standard deviations) demonstrating the effects of moderate-to-severe energy deficit on lean body mass were used to determine statistical power and sample size. The percentage total body mass loss (2.7 kg) attributed to lean body mass during a 21-d, higher-protein (1.6 g·kg $^{-1}$ ·d $^{-1}$ ), moderate energy deficit was approximately 30% (0.8 kg). However, the proportion of total body mass loss (5.8 kg) attributed to lean body mass in response to a short-term (~7-d), military training-induced, severe energy deficit was approximately 55% (3.1 kg) (unpublished data). Based on these results, and given the proposed study will induce a 55% energy deficit for 28 days in men consuming a higher-protein diet (1.6 g·kg $^{-1}$ ·d $^{-1}$ ), lean body mass will likely account for 40% of the total body mass loss. Maintaining testosterone within normal physiological ranges is expected to attenuate the loss of lean body mass by 25%, such that those assigned to the testosterone group will lose proportionally 30%, the same percentage of lean body mass as demonstrated in our previous study. Based on these estimates, the sample size necessary to determine the estimated differences between treatments is 22 per group. However, based on previous variability in lean body mass loss in response to moderate-to-severe energy deficit, 25 participants per group is a more conservative estimate to allow for detection of treatment effects in the current study. To account for possible attrition (20%), 30 participants will be assigned to each group (60 total participants). To successfully enroll 60 participants, we request the ability to consent up to 240 participants, given only a third of those briefed and consented in past projects, with more lenient study-specific eligibility criteria, were enrolled. **At least 50 participants will complete the intervention and enrollment will stop once 50 participants have completed the study.**

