**Table 2. Power Analysis and Sample Size Justification**

**Hypothesized Effect (mean  $\pm$  SD)**

$\Delta$ Lean body mass following the 28-d intervention, kg	
DEF	$3.0 \pm 0.75$
DEF+TEST	$2.25 \pm 0.75$
Effect Size	1.0
Alpha	0.05
Power	0.90
Sample Size	22 per group
Expected variability	25 per group
20% study attrition	60 participants total
75% eligibility screen failure	240 total consented individuals

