**Phase 1: Diet Acclimation (free-living). Day 0–Day 14**

- During the diet acclimation phase, participants will return to Pennington Biomedical once a day to eat and receive additional meals for the day. Participants will be weighed daily and caloric adjustments made if needed. Participants will be asked to record their activity daily throughout the phase. Additionally, 2 accelerometers (wrist- and waist-worn) will be applied at Day 0 and worn through day 14.
- Blood draws will occur on days 0, 7, and 14.
- Cognitive training will be performed on days 0, 2, 4, 6, 8, and 10 for approximately 1.5-2 hours each day. Cognitive testing will be performed on days 5 and 13 over a 2-hour period each day. The timing of training sessions is not critical.
- A DXA will be done on days 0 and 11.
- A 1-hour fMRI will be done approximately on days 5, 9, and 12.
- A food intake test with VAS and gut hormone assessments will be done on day 7.
- Participants will consume 150 mL/d  $^2\text{H}_2\text{O}$  (i.e., heavy water) from day 0 to 7 and 100 mL/d  $^2\text{H}_2\text{O}$  from day 8 to 14.
- Participants will be asked to provide a saliva sample on days 3, 7, and 11 to assess body water enrichment.
- Participants will ingest D3-creatine (D3Cr) (60 mg capsule) on day 11 for estimates of muscle mass at the end of phase 1 (urine collections on days 11, 13, 14).
- On day 11, participants will stay in the metabolic chamber and have urine nitrogen and urine creatinine collected for 24 hours.
- Participants will consume 2 g sucralose dissolved in 180 mL water on the morning of study day 11. A 24-hour urine sample collected with the nitrogen and creatinine testing will be used to analyze the sugar substitute ingestion.
- Participants will be asked to provide a stool sample on day 11 (+72 hours) for gut microbiome analysis.
- Information regarding adverse events will be collected on days 0, 7, and 14.
- A biodex familiarization test will be performed on day 0 and the actual biodex test will be performed on day 13.
- A VO2max treadmill test will be performed on day 0. The test will be used to prescribe exercise intensities.
- Eating Inventories (TFEQ, FCI, FCI trait) will be completed on day 14.
- A bike familiarization ride will be performed within the first week of Phase I. The familiarization ride will be used to establish appropriate settings and exercise workloads for the experimental testing procedures.

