- Muscle biopsies will be collected at rest on day 28 and pre, 60 min and 360 min post a 60 min cycle ergometry exercise session on day 42. **Participants will undergo 7 total muscle biopsy procedures during the entire study period (3 on one leg and 4 on the opposite leg, 3 total incisions).**
- Participants will ingest D3-creatine (D3Cr) (60 mg capsule) on day 39 for estimates of muscle mass at the end of phase 2 (urine collections on days 39, 41, 42).
- On day 39, participants will stay in the metabolic chamber and have urine nitrogen and urine creatinine collected for 24 hours.

- Participants will consume 2 g sucralose dissolved in 180 mL water on the morning of study day 39. A 24-hour urine sample collected for nitrogen and creatinine testing will be used to analyze the sugar substitute ingestion.
- Exercise testing for muscular strength (biodex) will be performed on day 41.
- Participants will be asked to provide a stool sample on days 25 and 39 (+72 hours) for gut microbiome analysis.
- Information regarding adverse events will be collected weekly on days 21, 28, 35, and 42.
- Participants will reside in the metabolic ward at PBRC during phase 2, thus the time commitment for this phase is 24 hours per day.
- Upon completion of each week of Phase 2, participants will receive an incentive item to aid in retention and adherence to the study protocol. Incentive items include a towel, water bottle, t-shirt, and gym bag.

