#### Determination of body composition

Height will be measured using a stadiometer. Weight will be measured (semi-nude and performed after an overnight fast) at PBRC using a calibrated digital scale at SV1 and

SV2 and daily during phase 1 and phase 2. After completing phase 2, participants will report to PBRC approximately once a week to weigh in and each participant will be provided a scale to take home for daily weight measurements (semi-nude and performed after an overnight fast).

Body composition will be determined using DXA (GE iDXA) on days 0, 11, 28, 39, 53 and EOS. Volunteers will undergo 6 DXA scans. DXA allows the non-invasive assessment of soft tissue composition by region with a precision of 1-3%. Volunteers lay in the supine position on the densitometer table in shorts, t-shirts, and socks. They will be asked to remain motionless for the 5-10 min scan. These data will be used to calculate lean body mass, fat mass, bone mineral content, bone mineral density, and total body tissue mass. Calibration to external standards will be performed prior to actual data collection.

Estimates of skeletal muscle mass will be determined using the creatine (methyl-d3) dilution method. The creatine dilution method uses basic principles of muscle creatine and creatinine biology to estimate muscle mass based on the irreversible conversion of creatine to creatinine and subsequent excretion in the urine. Participants will provide a fasting urine sample (to correct for background enrichments; **all urine samples will be second morning void before eating**) prior to ingesting a single, 60 mg dose (capsule) of D3Cr on days 11, 39, 53, and EOS. Fasting urine samples will be collected 48 and 72 hours after each creatine pill ingestion to assess longitudinal changes in muscle mass. Research staff will provide labeled tubes for each urine collection. De-identified urine samples will be processed and frozen for future analysis by liquid chromatography–mass spectrometry (LCMS).

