An indwelling intravenous catheter into the antecubital vein or forearm of the participant's arm will be placed 30 min prior to the breakfast meal. A fasted blood sample will be taken 15 min before beginning the meal. Blood will be sampled according to the timelines in **Tables 3 and 4**. At each time point 14.5 mL blood will be collected for a total of 275.5 mL over the full study to measure endocrine mediators of appetite. If at any point during the testing period the catheter becomes clogged or is no longer patent it will be removed and replaced. Serum will be analyzed for leptin and insulin (measured at -15 min only), serum for glucose, and plasma for acyl ghrelin and des-acyl ghrelin at PBRC using commercially available assays. Additional samples will be collected at each timepoint and archived for future tests. All samples will be collected using appropriate preservatives to minimize degradation. Blood measure collection time points are shown in **Appendix E**.

Determination of gut microbiome composition and activity, and intestinal permeability  
A single fecal sample will be collected at 4 time points (end of run-in diet [days 11-14], mid-point [days 25-28] and end of intervention [days 39-42], and upon return to initial body weight [EOS-EOS+3]) during the study to assess gut microbiota composition and function. At each time point participants will be given a ≤72-h window to collect a usable sample. A usable sample is defined as being > 25g wet weight, and having been delivered to study staff within 12-h of defecation while being kept cold but not frozen from the time of collection to delivery. If a participant does not provide a usable sample within the timeframe noted above, the collection period will be extended until a usable sample is produced. To collect fecal samples, all participants will be given pre-labeled containers with covers and a plastic device to "hold" the container in the toilet. Participants will defecate into the collection container which will then be given to study staff. During free-living phases of the study participants will be given plastic sealable bags, a cooler and ice packs to store and transport the samples from home (**Appendix L**).

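### The sample size rests on one unadjusted test of the group difference in lean-mass change over the deficit, but the analysis plan specifies an omnibus interaction followed by Bonferroni-adjusted comparisons and never names that test

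*Combined protocol and SAP*

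**What the plan says.** **Sizing.** Table 2 gives the hypothesized effect for "Lean body mass following the 28-d intervention, kg": a loss of 3.0 kg in DEF and 2.25 kg in DEF+TEST, SD 0.75 kg in each, effect size 1.0, alpha 0.05, power 0.90. The Power analysis section concludes that "the sample size necessary to determine the estimated differences between treatments is 22 per group", then raises this to 25 completers per group. No multiplicity allowance is mentioned.

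**Analysis.** Under Objective I: Statistics, Physiological outcomes, one generic mixed model is used "to test the effects of testosterone maintenance on changes in body composition" and all other physiological outcomes. It has subject as random, with study day, group and day-by-group as fixed. If the interaction reaches P < 0.05, "all possible within- and between-group comparisons will be completed, and the familywise error rate adjusted using the Bonferroni correction". The paragraph does not name LBM, a baseline day, an end-of-deficit day, the days in the model or the number of comparisons in the family.

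**Scans.** "Body composition will be determined using DXA (GE iDXA) on days 0, 11, 28, 39, 53 and EOS". The deficit runs from day 15 to day 42, so two scans precede it, two fall within it and two fall in recovery.

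**Nearby labels.** For D3-creatine, the Phase 1 list places the dose "on day 11 for estimates of muscle mass at the end of phase 1" and the Phase 2 list places it "on day 39 for estimates of muscle mass at the end of phase 2". The stool-sampling text uses "end of intervention [days 39-42". The statistics section does not carry these labels over to DXA.

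**Related text.** Randomization is stratified by age (under 29, or 29 and over), but the model has no age term. The Primary Study Endpoint section names total body mass, not LBM.

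**The concern.** Objective I-A asks whether testosterone attenuates the effects of the deficit, and LBM loss is the quantity that sets the sample size. A reader would expect the analysis section to contain the test that was powered. It contains a different procedure: an omnibus gate, then a set of adjusted pairwise comparisons of unspecified size.

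Two things are at stake. First, with more than two days in the model, a significant interaction says only that the group profiles differ somewhere. If the recovery scans enter, the result can come partly from recovery, which is Objective I-B. Second, the comparison that does address the deficit period is then judged at 0.05 divided by a number that the plan does not state. The power claimed in Table 2 may not apply to it, and the threshold stays open until someone chooses the scan days and counts the comparisons.

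**Working it through.** **1. Reproduce the plan's figure.** Inputs from Table 2: difference 3.0 − 2.25 = 0.75 kg, SD 0.75 kg, so d = 1.0. The test is two-sided at 0.05 (Objective I: Statistics) with power 0.90.

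n per group = 2(z₀.₉₇₅ + z₀.₉₀)²/d² = 2(1.960 + 1.282)² = 21.01, rounded up to 22.

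The noncentral t at 22 per group gives 0.8997, or 0.90. A one-sided test would need 18. The stated 22 is therefore one unadjusted two-sided comparison of change, and it is correct for its inputs.

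**2. Power at the planned 25 per group.** Noncentrality = d√(n/2) = √12.5 = 3.54 on 48 df. For a Bonferroni family of K, the two-sided level is 0.05/K.

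| K | Level | Critical t | Power |
|---|---|---|---|
| 1 | 0.05 | 2.011 | 0.934 |
| 2 | 0.025 | 2.314 | 0.885 |
| 4 | 0.0125 | 2.595 | 0.822 |
| 25 | 0.002 | 3.269 | 0.606 |

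Any family of two or more puts this contrast below 0.90.

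**3. Where such families could come from.** These counts are illustrations; the plan gives none. Take change from baseline as the outcome, so that the baseline scan drops out.
- Two scans leave one between-group comparison: K = 1.
- Three scans leave two change days. Two between-group comparisons alone give K = 2; adding one within-group comparison per group gives K = 4.
- Six scans leave five change days. Five between-group and 2 × 10 within-group comparisons give K = 25.

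**4. The interaction gate.** Assume compound symmetry with residual variance 0.75²/2 = 0.28125, which makes the SD of change 0.75 kg. Let δₜ be the assumed group difference on day t. The noncentrality is (n/2)Σ(δₜ − δ̄)²/0.28125, with k − 1 and 48(k − 1) df for k days. At 25 per group:

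| Days in model | Assumed δₜ (kg) | Noncentrality | Power |
|---|---|---|---|
| 11, 39 | 0, 0.75 | 12.5 | 0.934 |
| 11, 28, 39 | 0, 0.375, 0.75 | 12.5 | 0.886 |
| 0, 11, 28, 39 | 0, 0, 0.375, 0.75 | 17.2 | 0.944 |
| All six, fading | 0, 0, 0.375, 0.75, 0.375, 0 | 20.8 | 0.956 |
| All six, persisting | 0, 0, 0.375, 0.75, 0.75, 0.75 | 30.2 | 0.995 |

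In the two-day row the interaction is exactly the powered test. In the six-day rows part of the noncentrality comes from the recovery scans.

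**5. Gate and contrast together.** In a simulation of 20,000 trials with three scans, the probability of passing both was 0.880 with no adjustment and 0.822 at K = 4. The second figure equals the adjusted contrast alone, so once there is adjustment, the Bonferroni step rather than the gate accounts for the loss.

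**6. Which days.** Day 28 is described as the mid-point of the intervention in the biopsy section, and day 53 is in recovery. Day 39 is thus the only DXA near the end of the deficit, three days before it ends on day 42. The open choice is the baseline: day 0 or day 11.

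**The case against.** The strongest reply is that the interaction may be the intended test. In a model of days 11 and 39 only, it has 1 df, is tested at 0.05 before any Bonferroni step, and has 0.934 power. A loss of power is therefore not certain. This stands, and the point is conditional on it. But the plan does not restrict the model to two days, and six scans are scheduled.

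It can also be said that the gate is adequately powered, that Bonferroni changes a threshold rather than an estimate, and that the family might be formed per day, leaving one between-group comparison and no penalty. All three are fair. The third shows that the outcome depends on a choice the plan leaves unmade.

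Four stronger readings are tempting, and the documents do not support them:
- **The trial is too small.** A larger sample size can be computed for any assumed family, but the family sizes are the reader's constructions. The planned 25 per group suffices for the contrast that was powered.
- **LBM levels will be compared, with almost no power.** That needs a between-person SD, which the documents do not give, and the plan's wording points to changes.
- **Both ends of the contrast are undefined.** Only the baseline scan is truly open.
- **Omitting age stratum inflates type I error.** It is a mismatch between design and analysis, usually slightly conservative. Its effect on precision cannot be computed from the documents.

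**Conclusion.** The concern holds as a mismatch between the powered test and the written analysis. The sample-size arithmetic is right. If the model has exactly two days, or if the contrast is tested unadjusted and without the gate, power is 0.93 at 25 per group and nothing is lost. If more days enter and the follow-up is adjusted as written, the contrast that answers Objective I-A has power 0.885 for a family of two, 0.82 for four, and less for larger families. The documents do not fix how much less.

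These figures take the Table 2 effect and SD as given. The gate figures rest further on assumed compound symmetry and assumed profiles over time. The harm is conservatism, loss of the stated power, and room to choose scan days and family after seeing data. It is not a false-positive problem. It should be fixed; confidence is moderate because the size of the loss depends on how the text is read.

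**What to change.** In Objective I: Statistics, Physiological outcomes:

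- Specify the group difference in LBM change from a named pre-treatment DXA (day 11, or day 0 if preferred) to day 39 as one model contrast, tested at two-sided 0.05, outside the Bonferroni family and not conditional on the interaction. Note that day 39 is the last deficit-phase scan and precedes the end of the deficit on day 42.
- State which DXA days enter the model.
- Include the age stratum used at randomization as a fixed factor.
- Label the other LBM time-point comparisons exploratory, express them as differences in change, and state the size of their family.
- State how this contrast relates to total body mass, so that there are not two competing primary outcomes.

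The cost is SAP wording and a small change to model code, with no new data or visits. With the contrast tested alone, power at the planned 25 per group is 0.93. The downside is that the remaining LBM comparisons become explicitly exploratory.
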